8. RESEARCH QUESTION AND OBJECTIVES

The objective of the BEXSERO Pregnancy Registry is to evaluate pregnancy outcomes among women immunized with the BEXSERO vaccine within 30 days prior to the LMP or at any time during pregnancy. The primary outcomes of interest include major congenital malformations (MCMs), preterm birth, and low birth weight (LBW).

Other pregnancy outcomes will be collected, including stillbirths and spontaneous abortions (SABs). The probability of SAB varies greatly as a function of when the pregnancy is enrolled in the registry ([Savitz, 2002](#)). Because pregnancies will be reported to the registry at different and imprecise times during gestation, calculation of the prevalence of SAB from the registry is deemed inappropriate and could lead to erroneous conclusions. For example, if a woman enrolls in the registry at 16 weeks of pregnancy, only an SAB after this time could be detected and included in prospective reports. Similarly, SABs occurring earlier in gestation may not have been recognized and/or reported.

This registry is primarily descriptive and designed to detect potential safety signals rather than test hypotheses.

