9.7 Data Analysis

Registry Case Management and Disposition

Prospective Registry Reports

The registry will encourage prospective registration, which is defined as registration of a pregnancy exposure prior to knowledge or perceived knowledge of the pregnancy outcome (e.g., structural defect or genetic abnormality noted on a prenatal test). Those with no abnormalities identified on a prenatal test prior to enrollment will be considered prospective and included in the analysis. The rationale, potential bias, and analytic techniques to address any bias that may be introduced by this practice are addressed in [Section 9.7.4](#).

Data from HCP networks and HMOs that provide de-identified data on all exposed pregnancies in their network will fall into the category of prospective registry reports, as these networks/HMOs provide objective data on every pregnancy exposure in the network/HMO, both positive and negative outcomes. Thus, they avoid the reporting bias inherent in retrospective reporting only after a negative outcome has been noted.

Retrospective Registry Reports

Retrospective reports will also include subjects for whom the pregnancy outcome has already occurred or an abnormality has been identified on a diagnostic or screening prenatal test prior to enrollment. Retrospective reports can be biased toward the reporting of more unusual and severe cases and are less likely to be representative of the general population experience than reports reported prior to knowledge of outcome. Therefore, retrospective reports will not be included in the primary analysis and statistical calculations. Retrospective reports with reported MCMs and/or spontaneous fetal losses will be reviewed to aid in detection of early signals and listed in registry reports. Retrospective reports will not be actively solicited by the registry and will not be captured in the registry database unless a congenital anomaly is reported.

Loss to Follow-up

For a prospective report or pregnancy where follow-up information on the pregnancy outcome (live birth, fetal loss, etc.) is never obtained or is unavailable, the pregnancy will be considered lost to follow-up. Subjects lost prior to pregnancy outcome will be tallied in the registry reports but not included in the statistical analyses.

Duplicate Registry Reports

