The primary population for analysis will include prospective evaluable participants exposed to BEXSERO that are not lost to follow-up (i.e., participants with appropriate outcome information that meet the minimum criteria for evaluation). Because early prenatal testing is so frequent, it may be difficult to achieve adequate numbers of prospectively identified pregnant women if all pregnancies with prior prenatal testing are excluded from the analysis. Therefore, the primary analysis will include pregnancies enrolled prior to outcome but after prenatal testing as long as the test does not indicate the presence of an abnormality.

Exclusions for Analysis Purposes

Invalid registry reports and pregnancies deemed lost to follow-up will be excluded from the primary analysis. Retrospective reports will not be included, although retrospective

cases with MCMs will be reviewed and reported separately for signal detection purposes. In the event that it cannot be ascertained to which meningococcal B vaccine the woman was exposed, an unknown exposure cohort will be established and analyzed separately.

Sequential Pregnancies

The number and outcome of sequential pregnancies will be noted and presented. Sequential pregnancies will be included in the analytic dataset.

Multiple Gestation Pregnancies

The number, type (e.g., twin, triplet), and outcome of multiple gestation pregnancies will be noted and presented. Multiple gestation pregnancies will be included in the analytic dataset.

General Considerations for Data Analyses

This study is observational, and epidemiological methods will be employed for data collection and analyses.

Descriptive analysis will be performed for all prospective, evaluable data. The summary statistics for continuous and categorical variables to be used will be specified in the statistical analysis plan (SAP) but may include means, standard deviations, medians, minimums, maximums, percentiles, frequencies, and percentages. For analyses of associations between pregnancy outcomes and BEXSERO exposure, confounding and effect modification will be evaluated descriptively.

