9.7.3 Statistical Methods

Overall and stratum-specific point estimates and 95% confidence intervals will be calculated using the binomial distribution for prevalence estimates of MCMs, preterm birth, and LBW among pregnant women exposed to BEXSERO and their live births. For each prevalence estimate, both 1-sided and 2-sided 95% confidence intervals will be calculated and reported. One-sided confidence intervals are appropriate as we are specifically interested in detecting outcome prevalence estimates greater than their respective reference prevalence, and 2-sided confidence intervals will provide further description of the accuracy of the estimates.

Because most structural defects have their origins in the first trimester of pregnancy during the period of organogenesis, analyses of MCM will be stratified by trimester of exposure, if applicable. It is expected that the vast majority (99%) of prenatal exposures will occur during the first trimester before the pregnancy is recognized. The prevalence of combined MCMs reported to the registry will be calculated as a proportion with the number of MCMs as the numerator and the number of live births as the denominator. Pregnancy losses with reported MCMs occurring at or after 20 weeks' gestation will be included in the numerator of the estimate of risk for MCMs to increase sensitivity and to allow comparison of outcomes with the CDC MACDP, which calculates prevalence by this convention. A secondary analysis will be conducted including pregnancy losses with reported MCMs occurring at less than 20 weeks' gestation. The prevalence of combined MCMs in exposed cases will be compared with that of the CDC MACDP (Correa, 2007).

Only cases meeting the CDC MACDP criteria for a defect or with 2 or more conditional defects will be included in the primary analysis. Single minor defects do not constitute a MCM according to the CDC MACDP classification; therefore, they will be listed in the report, but not included in the primary analysis.

The prevalence of preterm births and LBW will be calculated as proportions, with the number of live births as the denominator. These prevalence estimates in exposed cases will be compared with those of the CDC NVSS (Martin, 2015). Because MCMs are often associated with preterm birth and LBW, sensitivity analyses will be performed excluding infants with MCMs from the numerator and denominator when prevalence estimates are determined for these outcomes.

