Formulas for the calculation of prevalence of the primary outcomes are presented below:

$$\begin{aligned} \text{MCM prevalence} &= \frac{\text{Number of live births and fetal losses occurring at } \geq 20 \text{ weeks gestation with MCM}}{\text{Number of live births (all fetal losses excluded from denominator per MACDP convention)}} \\ \text{Preterm birth prevalence} &= \frac{\text{Number of preterm live births}}{\text{Number of live births}} \\ \text{LBW prevalence} &= \frac{\text{Number of LBW live births}}{\text{Number of live births}} \end{aligned}$$

The MCM outcome data will be stratified by the earliest trimester of exposure to BEXSERO[®]. For this registry, gestational weeks are estimated from the most reliable EDD as reported by the HCP. If a CEDD is provided by the HCP, it will be used instead. The date of conception will be calculated as the most reliable EDD minus 38 weeks. If the EDD is not available or never estimated, the first day of the LMP may be used to estimate gestational age. The second trimester will be considered to begin at week 14, and the third trimester, at week 28. If there is a discrepancy between gestational age calculated from the LMP and reported gestational age, the HCP will be asked to verify the data.

If it is feasible, descriptive comparisons between the registry and an appropriate internal and/or external comparison group will be examined (see Section 9.2.3 for a description of potential reference groups).

Methods to Control for Confounding and Effect Modification

For analyses of associations between pregnancy outcomes and BEXSERO exposure, confounding and effect modification will be evaluated descriptively. A detailed description of these analyses will be available in the SAP. Potential confounders/effect modifiers may include the following:

- Maternal characteristics (e.g., age, ethnicity, race)

- Previous pregnancy outcomes (e.g., MCMs, stillbirth)
- Pregnancy complications (e.g., preterm labor, eclampsia, placental abruption)
- Comorbidities (e.g., diabetes, hypertension)
- Concomitant exposures (e.g., medications, alcohol, tobacco)
- Infant/fetus sex

Subgroup Analyses

Analyses will be stratified by trimester of exposure and other subgroups of interest, potentially including number of doses of BEXSERO received, gestational age at enrollment and maternal age. Additional details on subgroup analyses will be described in the SAP. Comparisons may be made to external cohorts, if appropriate.

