9.7.4 Statistical Considerations

Because early prenatal testing is so frequent, it may be difficult to achieve adequate numbers of prospectively identified pregnant women if all pregnancies with prior prenatal testing are excluded from the analysis. Therefore, the primary analysis will include pregnancies enrolled prior to outcome but after prenatal test as long as the test does not indicate an abnormality. However, this practice could potentially bias the results by lowering the overall risk of MCMs (Honein, 1999). The analysis will attempt to determine bias introduced by this practice by examining the data with and without these cases.

While the registry analysis will be limited primarily to prospective reports, some pregnancy exposures will be reported only following pregnancy outcome (retrospective cases). Each retrospective report will be carefully reviewed. In general, retrospective reports of exposures to vaccines or medication following notification of outcome are biased toward reporting of the severe and unusual cases and are not reflective of the general experience with the vaccine or medication. Moreover, information about the total number of exposed persons is not known. Therefore, prevalence estimates of outcomes cannot be calculated from these data. However, a series of reported MCMs can be analyzed to detect patterns of specific MCMs and can identify early signals of vaccine or medication risks.

Those pregnancies that have reached EDD, but for which outcome information was unobtainable after 4 attempts, will be considered lost to follow-up. It is possible that outcomes among pregnancies lost to follow-up could differ from those with documented outcomes. Because of differences in individual reporting patterns, it is currently not possible to assess with any certainty what impact the potential biases the losses to follow-up may have on the analysis. However, efforts at comparing some of the characteristics of

each group may be conducted in an attempt to assess this potential source of bias (details to follow in the SAP).

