When an analysis includes data from an external comparator, it is important to thoroughly understand the methodology of the external comparator and to take this into consideration when designing the analysis plan (Kennedy, 2004). As such, MACDP convention will be followed for the calculation of MCM prevalence: only live births of 20 weeks of gestation or greater will be included in the denominator. Fetal losses (SABs, IABs, stillbirths, etc.) with or without detected MCMs will be excluded from the denominator. The MACDP excludes fetal losses from the denominator to maintain consistency over time, as fetal death records were unavailable prior to 1994. In addition, the inclusion of fetal losses in the denominator may introduce classification bias. The percentage of these pregnancies consisting of potentially normal outcomes or MCMs is unknown. The data collection form attempts to obtain information on MCMs detected at the time of the outcome. However, the reporting physician may not know the condition of the aborted fetus. It is acknowledged that including only live births in the denominator is likely to overestimate the defect prevalence; however, there is only a small difference between prevalence estimates calculated using only live births versus live births plus fetal losses in the denominator given that the number of fetal deaths that are reported are a small proportion of the pregnancies 20 weeks or greater (Correa, 2007).

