9.9 Limitations of the Research Methods

Since participation in the registry will be accomplished in 3 ways (through voluntary self-enrollment by the pregnant women, through HCP enrollment on behalf of the woman with her consent, or finally, through the collection of de-identified data from HCPs within a network/HMO), the included subjects may not be representative of the overall population of US pregnant women. If possible, a sensitivity analysis will be conducted according to pregnant women's method of enrollment: the data collected from pregnant women who provide consent and either self-enroll or authorize their HCPs to enroll them in the registry will be examined separately from the de-identified data collected from HCPs on pregnancy exposures and outcomes within a network/HMO.

Additionally, it is possible that even in prospectively reported cases, potential bias could exist. For example, high-risk pregnancies or low-risk pregnancies may be more likely to be reported. It is also possible, and entirely likely, that differences in the prevalence estimates of pregnancy outcomes will be observed due to random variability (NBDPN, 2004). With the prevalence of the outcomes of interest being relatively low, cases of a particular outcome can be expected to be quite rare, and the coincidence of 2 or more cases in time may be just that: a coincidence. Confidence intervals will be carefully examined in order to assess the potential role of random variability.

Furthermore, it will be important to rule out other explanations for changing prevalence over time, including changes in medical diagnoses and technologies, changes in reporting and case ascertainment, and changes in the population at risk. In order to minimize the effect of these changes, the most current prevalence estimates available at the time of reporting for the population of interest will be used for analyses.

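### The preterm-birth denominator counts women who enroll at 37 weeks or later, who can no longer have a preterm birth, so late enrollment biases this primary estimate low against the NVSS reference

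*Combined protocol and SAP*

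**What the plan says.** - **Denominator and comparator.** Section 9.7.3 and the Data Analysis part of the abstract: "The prevalence of preterm births and LBW will be calculated as proportions, with the number of live births as the denominator". The formulas in 9.7.3 repeat this, and the estimate is compared with NVSS. Section 9.5 gives the reference as 11.71% for mothers under 25. Section 9.3.2 defines preterm birth as birth before 37 weeks.
- **Entry.** Section 9.7 defines prospective registration as "registration of a pregnancy exposure prior to knowledge or perceived knowledge of the pregnancy outcome". Under Analysis Population it adds that "the primary analysis will include pregnancies enrolled prior to outcome but after prenatal testing", provided the test shows no abnormality. Neither these passages nor the enrollment criteria in 9.2.3 set an upper gestational age.
- **Entry time elsewhere.** Section 8 declines to calculate spontaneous-abortion prevalence because women enroll at varying times; for a woman entering at 16 weeks, "only an SAB after this time could be detected and included in prospective reports". Section 9.7.4 says that including women enrolled after a normal prenatal test may lower the MCM risk, and adds: "The analysis will attempt to determine bias introduced by this practice by examining the data with and without these cases".
- **Comparator method.** Section 9.7.4 says "it is important to thoroughly understand the methodology of the external comparator and to take this into consideration when designing the analysis plan", and then works this out for MCM only.
- **Optional analyses.** The subgroups in 9.7.3 are described as "potentially including number of doses of BEXSERO received, gestational age at enrollment and maternal age". Section 9.9 on enrollment route: "If possible, a sensitivity analysis will be conducted according to" the method of enrollment.

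**The concern.** A pregnancy still ongoing at 37 weeks has already escaped preterm birth. If the woman enrolls at that point, her infant is a certain non-event in a proportion that is meant to estimate risk over the whole pregnancy. NVSS counts births whatever the timing of any contact with a registry, so the two proportions do not measure the same thing. Section 8 accepts this reasoning for spontaneous abortion, but nothing carries it over to preterm birth, which is a primary outcome.

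The direction matters because 9.7.1 and 9.7.3 state an interest in prevalence above the reference. A dilution of this kind works toward missing a signal. Preterm birth also has the smallest detectable ratio at every sample size in Table 9.5-1, and one termination criterion in section 13 turns on whether a 2-fold increase in at least one major outcome can be detected.

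Low birth weight has the same denominator and is biased in the same direction, but less, because it is defined by weight alone and a term infant can qualify. Network or HMO reports that cover every exposed pregnancy do not depend on when a woman chose to enroll and are largely unaffected.

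**Working it through.** **Inputs from the protocol (9.5, 9.6.2, Table 9.5-1).** Exact one-sample binomial, one-sided 5%, 80% power, reference p0 = 0.1171. Detectable ratios R for preterm birth: 3.13 (N=20), 2.24 (N=50), 1.79 (N=100), 1.63 (N=150).

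**Assumed input.** f, the share of live births from women enrolled at 37 weeks or later. The documents give no distribution of gestational age at enrollment, so a range is shown.

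**Step 1: reproduce the plan's figures.** The critical count r is the smallest count with P(Bin(N, p0) ≥ r) ≤ 0.05. This gives r = 6, 11, 18 and 25 for N = 20, 50, 100 and 150. Power at the tabled ratios is 80.0%, 79.8%, 80.1% and 80.3%. The table is arithmetically correct. The question is whether its reference suits a denominator that includes late entrants.

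**Step 2: bias.** Expected prevalence = (1 − f) × true prevalence.

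| f | True 11.71% is estimated as | True ratio 1.79 appears as |
|---|---|---|
| 5% | 0.95 × 11.71 = 11.1% | 1.70 |
| 10% | 0.90 × 11.71 = 10.5% | 1.61 |
| 20% | 0.80 × 11.71 = 9.4% | 1.43 |

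**Step 3: power.** Let m = N(1 − f) be the births still at risk at entry.

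- As written: P(Bin(m, R·p0) ≥ critical count for N).
- Restricted to enrollment before 37 weeks: P(Bin(m, R·p0) ≥ critical count for m).

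N = 100, R = 1.79, critical count as written 18:

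| f | m | Critical count for m | As written | Restricted |
|---|---|---|---|---|
| 2% | 98 | 18 | 77% | 77% |
| 3% | 97 | 18 | 76% | 76% |
| 5% | 95 | 17 | 72% | 80% |
| 10% | 90 | 17 | 63% | 72% |
| 20% | 80 | 15 | 41% | 73% |

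The restricted column is uneven because the critical count moves in whole steps. At f = 10%, power drops by 80.1 − 63.0 = 17.1 points; the restriction recovers about 9.5, and the other 7.6 are information lost. At f = 20%, about 32 of 39 points are recovered.

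Other sample sizes, as written vs restricted:

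| N, R | f = 10% | f = 20% |
|---|---|---|
| 150, 1.63 | 60% vs 76% | 35% vs 71% |
| 50, 2.24 | 66% vs 78% | 49% vs 76% |

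At N = 20 (R = 3.13) there is no difference at f = 5% or 10%: 75% and 70% either way.

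**Step 4: mixed routes.** If half the live births came from complete-capture networks (assumed), late entry of 10% or 20% among the rest gives an overall f of 5% or 10%.

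No figure is given for low birth weight, because the documents do not state what share of such births is preterm.

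**The case against.** **Size is unknown.** No passage gives f, and the large power losses need one live birth in ten or five to be enrolled in the last weeks of pregnancy. The follow-up schedule, with a contact at about 24 weeks, suggests that earlier entry is expected. At f of 2–3% and N = 100 the restriction recovers no power. This stands as a limit on magnitude. It does not remove the mechanism: the schedule is not an entry limit, and the 99% early-exposure expectation in 9.5 and 9.7.3 concerns vaccination, not enrollment.

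**The with/without check in 9.7.4 may cover it.** Most women enrolling at 37 weeks will have had a prenatal test, so the dataset without tested women would drop many of them. But the bias named there is for MCM, the check leaves the primary preterm estimate as it is, and it would also discard early enrollees who had been tested.

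**Stratification may follow.** The protocol names gestational age at enrollment as a possible subgroup and defers detail to the SAP. As written, this and the enrollment-route split are optional, and neither alters the primary estimate.

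**Net direction is uncertain.** Section 9.9 allows that high-risk pregnancies may be over-reported, which could raise the estimate. That is a separate bias and no reason to leave this one in place.

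**Restriction is incomplete.** Women entering shortly before 37 weeks have already escaped earlier preterm birth, so the restricted powers above are upper bounds. Some of the recovery also reflects discreteness: at N = 100 and f = 5%, the exact one-sided error is 0.049 against 0.042 for the full 100. Both points stand, and the first is why a delayed-entry analysis is proposed. With very few births that analysis would say little.

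**Conclusion.** The concern holds and should be fixed. The denominator, the absence of an entry limit and the downward direction of this bias all follow from the protocol's text. The size rests on an assumed f: none if nobody enrolls at 37 weeks or later, and a proportional understatement of f otherwise. Across f of 5–20%, the plan's example of 100 live births and a 1.79-fold increase has 72% down to 41% power instead of 80%. These figures take every woman entering before 37 weeks to carry the full risk. At f of 2–3% the case for restriction is removal of bias, not power.

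**What to change.** 1. In 9.7.3 and the abstract, define the primary preterm-birth denominator as live births from pregnancies enrolled before 37 completed weeks; for complete-capture network or HMO reports, exposed before 37 completed weeks. Apply the same condition to the numerator and report the number excluded.
2. Make the analysis by gestational age at enrollment mandatory for preterm birth and low birth weight.
3. Keep the low-birth-weight estimate on all live births, and show next to it one restricted to enrollment before 37 weeks.
4. Add a delayed-entry (left-truncated) estimate of birth before 37 weeks as a sensitivity analysis, where numbers allow, to address entry shortly before the cut-off.

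The cost is protocol and SAP wording plus some programming. Registration date, EDD or CEDD, and gestational age at outcome are already collected. The preterm denominator becomes slightly smaller, and the primary result is unchanged if nobody enrolls late.

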Preterm birth: An infant born at gestational age <37 weeks

Low Birth Weight: An infant whose birth weight is <2500 g

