- Tobacco, alcohol, and illicit drug use during pregnancy

Pregnancy Follow-up

Around the end of the second trimester and in the month of the EDD, the ***Interim Pregnancy Follow-up Form*** and ***Pregnancy Outcome Form***, respectively, will be requested from the obstetric HCP.

Information Collected at Interim Pregnancy Follow-up and Pregnancy Outcome

Interim Pregnancy Follow-up at End of Second Trimester

Pregnancy Status

- Updates to EDD (i.e., CEDD)
- Subsequent prenatal tests (diagnostic or screening) performed and findings including the identification of congenital anomalies
- Pregnancy complications (preterm labor, eclampsia, placental abruption)
- Details of pregnancy outcome if pregnancy is not ongoing as described below

Other Exposures

- Concomitant medications and vaccinations
- Tobacco, alcohol, and illicit drug use during pregnancy

Additional Information Collected at Pregnancy Outcome

Fetal Outcome

- Pregnancy outcome (live birth, stillbirth, SAB, IAB, ectopic pregnancy, molar pregnancy)
- Date of outcome of pregnancy
- Gestational age at outcome
- Fetal/infant characteristics: sex, birth weight
 - MCM(s) and assessment of potential contributing factors
 - For a fetal loss (SAB, stillbirth), factors that may have had an impact on the fetal loss and attribution

Targeted Follow-up Process

If there is an MCM or other event of interest noted, in order to properly characterize the event, additional information may be requested from the reporting HCP on the **Targeted Follow-up Form**:

- Details of the MCM/condition
- Etiology
- Outcome attribution
- Specific questions requested by GSK and/or the MCM evaluator

Attempts to Obtain the Follow-up Information

In the month that the follow-up is due, the HCP will be contacted and asked to provide follow-up information. Three subsequent attempts, as necessary, will be made every 2 weeks via various modes of communication. If there is still no response from the provider, a final communication will be sent indicating the case is lost to follow-up. If this communication prompts a response from the HCP or the requested data is later received, the case will be re-opened and assessed for evaluability. If, at any point in the follow-up process, the reporter indicates that the patient is lost to follow-up, no further attempts will be made.

Follow-up Process for Clarification of Information

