
9.2 Does the protocol describe the information available from the data source(s) on:
 
8.2.1 Exposure? (e.g. date of dispensing, drug quantity, dose, number of days of supply prescription, daily dosage, prescriber)
 
8.2.2 Outcomes? (e.g. date of occurrence, multiple event, severity measures related to event)
 
8.2.3 Covariates? (e.g. age, sex, clinical and drug use history, co-morbidity, co-medications, life style, etc.)
	

 

 

	

 

 

	

 

 

	
9.4.1
 
9.4.2
 
9.4.3

9.3 Is a coding system described for:
 
9.3.1 Exposure? (e.g. WHO Drug Dictionary, Anatomical Therapeutic Chemical (ATC) Classification System)
 
9.3.2 Outcomes? (e.g. International Classification of Diseases (ICD)-10, Medical Dictionary for Regulatory Activities (MedDRA))
 
9.3.3 Covariates?
	

 

 

	

 

 

	

 

 

	
9.3
 
9.3
 
9.3

9.4 Is a linkage method between data sources described? (e.g. based on a unique identifier or other)
	

	

	

	

Comments:

The exposure (the vaccine) will be described by lot number where available.

Section 10: Analysis plan	Yes	No	N/A	Section Number
10.1 Is the choice of statistical techniques described?				9.7.3
10.2 Are descriptive analyses included?				4.7.3
10.3 Are stratified analyses included?				9.7.3
10.4 Does the plan describe methods for adjusting for confounding?				9.7.3

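### Preterm labor, eclampsia and placental abruption are listed as potential confounders, although for preterm birth and low birth weight they are events on the causal path after exposure

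*Combined protocol and SAP*

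**What the plan says.** Section 9.7.3, under the methods to control for confounding and effect modification, introduces its list with "Potential confounders/effect modifiers may include the following". One entry is "Pregnancy complications (e.g., preterm labor, eclampsia, placental abruption". It stands beside factors that precede vaccination, such as maternal age and previous pregnancy outcomes. The same paragraph says that "confounding and effect modification will be evaluated descriptively" and leaves the detail to the SAP. The document contains no further SAP text on the point.

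On timing, Section 9.7.3 states: "It is expected that the vast majority (99%) of prenatal exposures will occur during the first trimester before the pregnancy is recognized". Section 9.4 lists "Pregnancy complications (preterm labor, eclampsia, placental abruption" among the items for the interim follow-up at the end of the second trimester. They are not among the items collected at registration.

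On outcomes, preterm birth and LBW are primary. Section 9.3.2 gives "Preterm birth: An infant born at gestational age <37 weeks". For the estimates, Section 9.7.3 says: "The prevalence of preterm births and LBW will be calculated as proportions, with the number of live births as the denominator".

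The ENCePP checklist (Appendix 2, item 10.4) asks "Does the plan describe methods for adjusting for confounding". It is answered yes, with Section 9.7.3 as the reference.

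**The concern.** A confounder must not be a consequence of the exposure. By the protocol's own timing, a woman vaccinated before or soon after conception has her preterm labor, eclampsia or abruption later. If the vaccine raised the risk of preterm birth, preterm labor is one of the most direct ways it would do so. Comparing women with like complication status then removes part of the effect under study. Calling the variable an effect modifier does not help, because stratifying on a consequence of exposure has the same problem.

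What is at stake is how an excess is interpreted. The registry exists to detect signals. Section 9.7.2 says baseline data will be reviewed for confounding factors that could affect the comparison with reference prevalences, and Section 9.7.3 names the candidates. If preterm births are more frequent than the reference and many of those women had preterm labor, the list as written invites the conclusion that a confounder accounts for it. Nothing in the protocol separates factors fixed before exposure from events after it.

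**Working it through.** **Inputs from the protocol (Sections 9.5 and 9.6.2, Table 9.5-1).** Reference prevalence p0 is 11.71% for preterm birth and 8.50% for LBW. The test is a one-sample binomial, one-sided 5%, with 80% power. At n = 100 live births the detectable ratios are 1.79 and 1.96.

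**Step 1: reproduce the plan's figures.** Find the smallest r with P(X ≥ r | n = 100, p0) ≤ 0.05, then compute P(X ≥ r) at ratio × p0.

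- Preterm birth: r = 18, exact type I error 0.042 (r = 17 would give 0.073). At 1.79 × 11.71% = 20.96%, power is 0.80.
- LBW: r = 14, exact type I error 0.044 (r = 13 would give 0.082). At 1.96 × 8.50% = 16.66%, power is 0.80.

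Both agree with the table. The power figures are correct and are not in dispute.

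**Step 2: what remains after conditioning on the complications.** Let RR be the true ratio and s the share of the excess that arises because exposure makes the complications more frequent. That shift alone multiplies prevalence by 1 + s(RR − 1). Assume the rest of the effect is a uniform relative increase within complication strata. Holding complications at their reference distribution then leaves

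remaining ratio = RR / [1 + s(RR − 1)].

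For preterm birth at s = 0.50 this is 1.79 / (1 + 0.50 × 0.79) = 1.79 / 1.395 = 1.28. Power is P(X ≥ r) at the remaining ratio × p0, treating the standardised prevalence as a simple proportion of 100.

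| Assumed share s | Preterm birth: ratio | Power | LBW: ratio | Power |
|---|---|---|---|---|
| 0 | 1.79 | 80% | 1.96 | 80% |
| 25% | 1.49 | 49% | 1.58 | 48% |
| 50% | 1.28 | 24% | 1.32 | 23% |
| 75% | 1.12 | 10% | 1.14 | 10% |
| 100% | 1.00 | 4% | 1.00 | 4% |

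The last row is the type I error: the signal is gone. The first row is also the crude comparison, which never conditions on complications and keeps its stated power.

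**What the table does not show.** The documents give no value for s, so the range is illustrative. They also specify no standardised or adjusted estimate. The table sizes what conditioning would do if it were carried out, formally or in the reader's reasoning.

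**The case against.** The strongest reply is that no planned analysis conditions on these variables. The preterm birth and LBW prevalences are crude proportions of live births, reported with confidence intervals whatever the complication data show. The list is permissive, the evaluation is descriptive, and no adjustment model is given. The subgroups named are trimester of exposure, number of doses, gestational age at enrollment and maternal age. None of the stated exclusions concerns complications; the one outcome-related exclusion for these endpoints is a sensitivity analysis omitting infants with malformations. The checklist's yes only points back to Section 9.7.3, which contains no adjustment method. All of this stands, and it confines the problem to the secondary interpretation.

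A reader might infer more: that preterm births following a complication would be set aside, so that a real signal is removed or even reversed. If 30%, 50% or 70% of registry preterm births were set aside and the remainder compared with the full 11.71%, the ratio would fall from 1.79 to 1.34, 1.00 or 0.63. The documents do not support that reading. No section proposes such a removal, and the fall comes from depleting only the registry side. With the same share removed from the reference as well, the ratios are 1.84, 1.88 and 1.93. Those figures should not be used to size this point.

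The reply is also right that the list serves every pregnancy outcome, including malformations. The argument here concerns preterm birth and LBW only, and the fix is limited accordingly. Finally, a descriptive review might itself notice that preterm labor was unusually frequent. That depends on the reviewer treating it as a finding, and the present label points the other way.

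A few women may be exposed after a complication, but on the protocol's own expectation exposures after the first trimester are about 1% of the total.

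**Conclusion.** The listing is wrong for preterm birth and LBW and should be corrected. For nearly all women these complications are intermediates, by the protocol's own timing of exposure and data collection. The primary estimates and their stated power are not affected. The harm is that the only confounding evaluation planned could attenuate a true excess or be read as explaining it away.

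It would be too strong to say that the signal will be removed. Complete loss requires the whole excess to run through the complications; with partial mediation the ratio is attenuated. At n = 100, power to see what remains is below 50% for both outcomes at every assumed share from 25% upward. This rests on the assumed shares, on a uniform relative increase within strata, and on conditioning actually taking place. The structural point needs none of these assumptions.

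**What to change.** In Section 9.7.3, and in the SAP text that builds on it:

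- Remove pregnancy complications from the confounder and effect-modifier list for preterm birth and LBW.
- Limit that list to factors fixed before exposure, such as maternal age, race and ethnicity, previous pregnancy outcomes, pre-existing conditions, and other exposures preceding vaccination.
- State that the preterm birth and LBW results will not be stratified on, restricted by, or discounted for preterm labor, eclampsia or placental abruption.
- Tabulate these three complications as additional descriptive outcomes. Section 9.4 names them at the interim follow-up and does not name them again among the additional items at pregnancy outcome, so the table should state the period it covers.

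The cost is one edited bullet, one added sentence and one more descriptive table from data already collected. The crude comparisons keep their stated 80% power.
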